### **3.3 Exploratory Objectives**

- 1) To perform analyses of tumor infiltrating lymphocytes (TILs) to identify changes in functional markers in response to the addition of itacitinib to pembrolizumab.
- 2) To perform gene expression studies of tumor tissue using Nanostring to characterize genetic effects in response to immunotherapy.

## **4.0 BACKGROUND & RATIONALE**

### **4.1 Background**

Non-small cell lung cancer (NSCLC) is the leading cause of cancer death in the United States [3]. More than half of patients present with metastatic disease, and are thus considered incurable [4]. Until very recently, the standard first-line treatment for NSCLC not harboring a targetable mutation was platinum doublet chemotherapy. While supportive care measures for patients receiving cytotoxic chemotherapy have improved markedly, the side effects of these agents can be substantial [5, 6]. Immunotherapy, most commonly using PD-1 inhibitors, is now known to have significant activity in NSCLC with a very favorable side effect profile [7-9]. Most recently, the KEYNOTE 024 study revealed that among patients with PD-L1 expression greater than or equal to 50%, pembrolizumab was associated with superior overall and progression free survival when compared with platinum doublet chemotherapy [1].

#### **4.1.1 Pharmaceutical and Therapeutic Background**

The importance of intact immune surveillance in controlling outgrowth of neoplastic transformation has been known for decades [10]. Accumulating evidence shows a correlation between tumor-infiltrating lymphocytes (TILs) in cancer tissue and favorable prognosis in various malignancies [11-15]. In particular, the presence of CD8+ T-cells and the ratio of CD8+ effector T-cells to FoxP3+ regulatory T-cells seems to correlate with improved prognosis and long-term survival in many solid tumors.

The PD-1 receptor-ligand interaction between tumor cells and the immune system is a major pathway hijacked by tumors to suppress immune control. The normal function of PD-1, expressed on the cell surface of activated T-cells under healthy conditions, is to down-modulate unwanted or excessive immune responses, including autoimmune reactions. PD-1 (encoded by the gene *Pdcd1*) is an Ig superfamily member related to CD28 and CTLA-4 which has been shown to negatively regulate antigen receptor signaling upon engagement of its ligands (PD-L1 and/or PD-L2) [16, 17]. The structure of murine PD-1 has been resolved [18]. PD-1 and family members are type I transmembrane glycoproteins containing an Ig Variable-type (V-type) domain responsible for ligand binding and a cytoplasmic tail which is responsible for the binding of signaling molecules. The cytoplasmic tail of PD-1 contains 2 tyrosine-based signaling motifs, an immunoreceptor tyrosine-based inhibition motif (ITIM) and an immunoreceptor tyrosine-based

CONFIDENTIAL

This material is the property of the University of Pennsylvania. Do not disclose or use except as authorized in writing by the study sponsor.

switch motif (ITSM). Following T-cell stimulation, PD-1 recruits the tyrosine phosphatases SHP-1 and SHP-2 to the ITSM motif within its cytoplasmic tail, leading to the dephosphorylation of effector molecules such as CD3 $\zeta$ , PKC $\theta$  and ZAP70 which are involved in the CD3 T-cell signaling cascade [19-22]. The mechanism by which PD-1 down modulates T-cell responses is similar to, but distinct from that of CTLA-4 as both molecules regulate an overlapping set of signaling proteins [23, 24]. PD-1 was shown to be expressed on activated lymphocytes including peripheral CD4+ and CD8+ T-cells, B-cells, Tregs and Natural Killer cells [25, 26]. Expression has also been shown during thymic development on CD4-CD8- (double negative) T-cells as well as subsets of macrophages and dendritic cells [17]. The ligands for PD-1 (PD-L1 and PD-L2) are constitutively expressed or can be induced in a variety of cell types, including non-hematopoietic tissues as well as in various tumors [23, 27-29]. Both ligands are type I transmembrane receptors containing both IgV- and IgC-like domains in the extracellular region and contain short cytoplasmic regions with no known signaling motifs. Binding of either PD-1 ligand to PD-1 inhibits T-cell activation triggered through the T-cell receptor. PD-L1 is expressed at low levels on various non-hematopoietic tissues, most notably on vascular endothelium, whereas PD-L2 protein is only detectably expressed on antigen-presenting cells found in lymphoid tissue or chronic inflammatory environments. PD-L2 is thought to control immune T-cell activation in lymphoid organs, whereas PD-L1 serves to dampen unwarranted T-cell function in peripheral tissues [23]. Although healthy organs express little (if any) PD-L1, a variety of cancers have been demonstrated to express abundant levels of this T-cell inhibitor. PD-1 has been suggested to regulate tumor-specific T-cell expansion in subjects with melanoma (MEL) [30]. This suggests that the PD-1/PD-L1 pathway plays a critical role in tumor immune evasion and should be considered as an attractive target for therapeutic intervention.

Pembrolizumab (previously known as MK-3475 and SCH 900475) is a potent and highly selective humanized monoclonal antibody (mAb) of the IgG4/kappa isotype designed to directly block the interaction between PD-1 and its ligands, PD-L1 and PD-L2.

Interferons are known to have an important role early in generating anti-tumor T cell responses. However, interferons are also involved in the development of adaptive immune resistance [31, 32]. Signaling through the JAK-STAT pathway, interferons regulate PD-L1 expression as well as multiple other negative feedback effects on the immune response through pathways that would not be inhibited by PD-1 blockade alone [33]. Interferon signaling has been theorized as an explanation for the observation that elevated PD-L1 expression is not universally associated with response to pembrolizumab and may also be responsible for primary or secondary treatment resistance [1, 34]. JAK1 is a tyrosine kinase necessary for signaling downstream of both type I and II interferon receptors, as well as multiple other inflammatory cytokines. JAK/STAT signaling has been proposed to promote tumor growth in part by promoting an inflammatory microenvironment that limits CD8+ T cell activity [35].

Itacitinib is a potent JAK1 selective small molecule inhibitor (half maximal inhibitory concentration [ $IC_{50}$ ] = 3.6 nM), with 22 to 500-fold greater selectivity for JAK1 compared to other JAK family members including JAK2, JAK3 and TYK2.

#### **4.1.2 Preclinical and Clinical Trial Data**

Previous work in a mouse melanoma model showed that tumor intrinsic interferon signaling promotes resistance to immune checkpoint blockade [36]. Knocking out type I and II interferon receptors on melanoma cells sensitizes them to immune checkpoint blockade, markedly improving treatment response and survival in pre-clinical models. T cells from these mice express higher proliferative and cytotoxic markers after immune checkpoint blockade.

CONFIDENTIAL

This material is the property of the University of Pennsylvania. Do not disclose or use except as authorized in writing by the study sponsor.

Preclinical studies utilizing a JAK1/2 inhibitor to block interferon signaling revealed the following observations that can be translated to human trials:

- JAK inhibition reduced tumor growth in response to immune checkpoint blockade and flow cytometry analysis of tumor cells demonstrated decreased surface expression of multiple inhibitory receptor ligands, which generally are associated with immune suppression.
- As prolonged JAK inhibition can have side effects, we tested a short course of JAK inhibitor therapy and still observed consistent improvements in tumor regression.
- When JAK inhibition began concurrently with checkpoint blockade, no improvement was seen in tumor regression relative to checkpoint blockade alone.
- When JAK inhibition was started after an induction phase of checkpoint blockade, however, a marked increase in tumor regression was seen. The selective benefit of sequential, as opposed to concurrent therapy initiation is consistent with 1) the immunostimulatory role of interferon signaling in early events of dendritic cell activation and T cell priming, and 2) the feedback inhibition and immunosuppressive role that occurs with prolonged interferon signaling.

The importance of the timing of JAK inhibition is also implied by studies in chronic viral infections. Blocking interferon signaling late in infection improves viral control, while earlier inhibition is not beneficial[37, 38]. In this study, we aim to extend these findings to patients by testing the addition of JAK inhibition to ongoing anti-PD-1 therapy. We hypothesize that combined treatment with pembrolizumab and itacitinib will be associated with an overall response rate of at least 55%. Moreover, using paired blood and tissue-based biomarkers during the course of treatment we hope to better understand the dynamics of response to immunotherapy among patients with NSCLC.

The combination of itacitinib and pembrolizumab is being evaluated in a phase I study in patients with advanced solid tumors. Data from this trial have not been presented or published. To date, 35 subjects have been treated in the dose escalation and expansion cohorts. No dose-limiting toxicities were noted. The risks of using itacitinib in combination with pembrolizumab are unknown at this time. We anticipate the risk profile of these agents when given in combination will be similar to that of the risk profile of each drug when given alone. Efficacy data is currently not available for this combination.

Refer to the Investigator's Brochure of itacitinib and the pembrolizumab package insert for additional Preclinical and Clinical data including information on potential toxicities.

## 4.2 Rationale

### 4.2.1 Rationale for the Trial and Selected Subject Population

The therapeutic benefit of immune checkpoint blockade has now been seen in multiple malignancies, with durable responses observed in a subset of patients [1, 9, 34, 39]. In spite of these exciting results, only a limited number of patients respond to PD-1 blockade, with response rates of approximately 20% in an unselected population. PD-L1 expression is the best-studied predictive biomarker for response to checkpoint blockade in NSCLC [40]. While PD-L1 is an imperfect biomarker, with significant dynamism and heterogeneity, a recent study of patients with tumors expressing a high level of PD-L1 (>50%) pembrolizumab was found to improve overall

CONFIDENTIAL

This material is the property of the University of Pennsylvania. Do not disclose or use except as authorized in writing by the study sponsor.

survival and progression free survival over platinum doublet chemotherapy in the first line treatment of NSCLC [1, 41] Even in this population enriched for patients likely to respond to PD-1 inhibition, the response rate to pembrolizumab was only 44.8%. While this is a great advance, there is clearly room for improvement as we attempt to extend the benefits of anti-PD-1 therapy to a larger patient population.

Patients with newly diagnosed stage IV or metastatic NSCLC with tumor PD-L1 expression greater than or equal to 50% will be enrolled in this study prior to any systemic therapy for metastatic disease. This patient population is selected because 1) PD-L1 is itself upregulated by interferon signaling and could serve as a biomarker for JAK1 inhibition, and 2) we hypothesize that in a proportion of patients with PD-L1+ tumors, feedback inhibition that occurs with prolonged interferon signaling limits response. Thus, patients with high levels of PD-L1 expression may be more likely to benefit from the combination of pembrolizumab and itacitinib.

#### **4.2.2 Rationale for Dose Selection/Regimen/ Modification**

The currently approved dose for pembrolizumab in patients with NSCLC is 200mg every 3 weeks. The 200mg every 3 week dose was also shown to be safe and effective in a first line treatment trial for patients with PD-L1 positive NSCLC [1]. At this time, the duration of treatment with pembrolizumab in patients with a clinical benefit is not clear but a standard practice is to continue treatment in the absence of adverse effects and/or clinical and radiographic disease progression. Therefore treatment with pembrolizumab will continue indefinitely in the absence of (1) documented disease progression per RECIST 1.1, (2) unacceptable adverse event(s), (3) intercurrent illness that prevents further administration of treatment, (4) investigator's decision to withdraw the subject, (5) subject withdrawal of consent, (6) pregnancy of the subject, (7) noncompliance with trial treatment or procedure requirements, (8) institution of alternative systemic treatment, or (9) other administrative reasons. Pembrolizumab may also continue at the physician investigator's discretion if the subject continues to benefit clinically from treatment.

In study INCB039110-107, 35 subjects with advanced solid tumors have been treated with itacitinib in combination with pembrolizumab (8 subjects in Part 1a [dose escalation] and 27 subjects in Part 1b [dose expansion]). The most frequently reported treatment-emergent adverse events (TEAEs) in Part 1a were anemia, fatigue, disease progression (50% each) and nausea, decreased appetite, and decreased weight (37.5% each). The most frequent TEAE in Part 1b were fatigue and nausea (37.0% each). There were no dose-limiting toxicities (DLTs) in Part 1a. The dose expansion cohort was treated with 300mg daily of itacitinib. Serious adverse events (SAE) were reported in 6 subjects in the expansion cohort and include disease progression (2 subjects, 7.4%) and abdominal pain, gastric obstruction, pancreatitis, pyrexia, urinary tract infection and pulmonary embolism (1 subject each, 3.7%). Only pyrexia was considered to be a treatment-related SAE.

Itacitinib is also being evaluated in combination with other immunotherapies in research studies. In personal communications with Incyte (the sponsor of these trials), they decided that based upon proprietary information, the recommended phase 2 dose for future study is 200mg/daily. As more precise data become available, the protocol and consent will be updated to better characterize adverse events.

CONFIDENTIAL

This material is the property of the University of Pennsylvania. Do not disclose or use except as authorized in writing by the study sponsor.

### **4.2.3 Rationale for Endpoints**

#### **4.2.3.1 Efficacy Endpoints**

##### **4.2.3.1.1 Primary**

Objective response rate, defined as the percentage of evaluable subjects who achieve a complete or partial clinical response at 12 weeks, according to RECIST 1.1 is the primary endpoint of this study. Given that this is a first line study of a novel combination, ORR was chosen as an earlier indicator of efficacy of the combination and to limit the number of subjects exposed if improved efficacy is not observed. Moreover, based on the mechanism of action, JAK1 inhibition would be predicted to improve the response rate in a population of patients with PD-L1 positive tumors by reducing the expression of additional immune inhibitory pathways in the tumor microenvironment. Responses will be compared to the subject's baseline assessment and historical controls using pembrolizumab monotherapy.

##### **4.2.3.1.2 Secondary**

Peripheral blood immune profiling will provide important mechanistic information on how PD-1 blockade and itacitinib function in human subjects. By studying treatment related changes in blood and tumor, and correlate these with response or resistance, superior and perhaps tailored combination treatment strategies could potentially be developed in the future. Correlative samples will be banked upon receipt and correlative assays performed in the following priority order.

High priority assays:

1. Multiparametric flow cytometry analysis of peripheral blood mononuclear cells to analyze T cell subsets and markers of functionality. T cell subsets will be determined using transcription factors and surface markers subsets. Functionality will be measured by examining activation markers, cytokines, effector molecules, and proliferation markers.
2. Transcriptomic analyses of tumor specimens to identify changes in gene expression after the addition of itacitinib to pembrolizumab. In particular, we will examine a subset of interferon-stimulated genes (ISGs) associated with resistance to checkpoint blockade in pre-clinical models.
3. Measurement of inflammatory cytokine or chemokine levels in subject serum. In particular, we will examine interferon levels and other cytokines regulated by the JAK1 pathway as biomarkers for both on-target drug activity and response.

Second priority assays:

1. Measurement of inflammatory cytokine or chemokine levels in subject serum. Circulating tumor cell (CTC) and circulating tumor DNA (ctDNA) measurements and profiling.

Additional secondary endpoints include progression free survival (PFS), overall survival (OS) and duration of response (DOR). PFS is defined as days from initiation of study therapy to first documented disease progression, death due to any cause or last subject contact which documents progression-free status. Those patients who are currently on-study and progression-free at 16 weeks, will no longer be followed and will be censored for PFS and OS at week 16. DOR is defined as the time from first documentation of partial or complete response to first documented disease progression. Those patients who are currently on-study and progression-free at 16 weeks, will no longer be followed and will be censored for PFS and OS at week 16.

CONFIDENTIAL

This material is the property of the University of Pennsylvania. Do not disclose or use except as authorized in writing by the study sponsor.

OS is defined as days from initiation of study therapy to death due to any cause or last subject contact. Those patients who are currently on-study and progression-free at 16 weeks, will no longer be followed and will be censored for PFS and OS at week 16.

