### **3.2 Secondary Objectives**

- 1) To collect paired blood and tumor tissue samples in order to perform mechanistic studies on treatment-related changes in the subject and tumor immune profiles
- 2) To determine the median progression free survival (PFS) and duration of response (DOR) at week 12 as well as overall survival (OS) for subjects treated with pembrolizumab and itacitinib, up week 16.

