5. RECIST 1.1 will be used in this study for assessment of tumor response. While either CT or MRI may be utilized, as per RECIST 1.1, CT is the preferred imaging technique in this study. Tumor imaging timing should follow calendar days and should not be adjusted for delays in cycle starts or extension of pembrolizumab cycle duration.
6. The End of Treatment (EOT) Safety Follow-up Visit will occur at Week 12 (+/-5d). The End of Study (EOS) Visit will occur at Week 16 (+/-10d). If the PI considers it beneficial for the subject, a fifth cycle may be administered prior to EOS visit. Subjects who remained on study treatment beyond Week 16 prior to the approval of Protocol Amendment V5, will be asked to undergo an End of Study Visit at their next clinic appointment prior to being withdrawn from the study. Please refer to **Section 7.1.6.1** for how to handle subjects who prematurely discontinue from study treatment.
7. Baseline tumor imaging to be performed within 30 days prior to Cycle 1/Day 1. A PET/CT may be used to fulfill baseline imaging requirements, however a PET/CT cannot be substituted for post-infusion imaging. Please refer to **Section 7.1.2.6** for additional information.

CONFIDENTIAL

This material is the property of the University of Pennsylvania. Do not disclose or use except as authorized in writing by the study sponsor.

8. Please refer to **Table 4** for additional information. After Cycle 1, pre-dose laboratory procedures can be conducted up to 72 hours prior to dosing. Results must be reviewed by the investigator or qualified designee and found to be acceptable prior to each dose of trial treatment.
9. Screening laboratory tests are to be performed within 10 days prior to Cycle 1/Day 1.
10. Performed 7-14 days after Cycle 2 of pembrolizumab. Tumor imaging will be used for biopsy planning only, and no treatment decisions will be made based upon the results.
11. Performed at the end of Cycle 4, before the end of study visit. Imaging performed at this timepoint will be used to evaluate objective response by RECIST 1.1.
12. An archived tumor tissue sample may be collected for exploratory analysis if available. Subjects will not undergo an additional procedure to obtain this sample. Please refer to the Lab Manual for additional instructions.

CONFIDENTIAL

This material is the property of the University of Pennsylvania. Do not disclose or use except as authorized in writing by the study sponsor.

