### **7.1.2.6 *Tumor Imaging and Assessment of Disease***

The initial tumor imaging will be performed within 30 days prior to the first dose of trial treatment. Scans performed as part of routine clinical management are acceptable for use as the screening scan if they are of diagnostic quality and performed within 30 days prior to the first dose of trial treatment. A PET/CT may be used to fulfill baseline imaging requirements; however a PET/CT cannot be substituted for post-infusion imaging.

As responses to immunotherapy may be delayed, no subjects should have treatment decisions modified by the week 6 scan ( $42 \pm 7$  days) alone – this is intended as a research scan to guide biopsies. A repeat scan at 12 weeks (performed at the end of Cycle 4 prior to end of study visit) is intended for the primary outcome and clinical decision-making. Tumor imaging timing should follow calendar days and should not be adjusted for delays in cycle starts or extension of pembrolizumab cycle duration.

If a subject demonstrates radiographic progression at Week 12, repeat imaging may be performed at least 28 days later at the discretion of the treating investigator in order to confirm radiographic progression.

The same imaging techniques should be used to follow a subject throughout the trial. For subjects with brain metastases, MRI brain should be included in the imaging follow up prior to treatment and at any time when a subject develops new neurologic symptoms.

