##### **Progression Free Survival (PFS)**

CONFIDENTIAL

This material is the property of the University of Pennsylvania. Do not disclose or use except as authorized in writing by the study sponsor.

Progression-free survival (PFS) is defined as days from initiation of study therapy to first documented disease progression, death due to any cause or last subject contact which documents progression-free status. Those patients who are currently on-study and progression-free at 16 weeks, will no longer be followed and will be censored for PFS at week 16.

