#### Duration of response (DOR)

Duration of response (DOR) is defined as days from first documented complete or partial clinical response to first documented disease progression. Those patients who are currently on-study and progression-free at 16 weeks, will no longer be followed and will be censored for DOR at week 16.

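### PFS and DOR are censored at week 16 but the last scheduled scan is at week 12, so the final four weeks of either curve rest on no planned tumor assessment

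*Combined protocol and SAP*

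**What the plan says.** **Censoring.** Section 4.2.3.1.2 provides that subjects still on study and progression-free at week 16 "will no longer be followed and will be censored for PFS and OS at week 16". Under Section 8.2.1, PFS in a subject without an event runs to the "last subject contact which documents progression-free status"; no scan is required. Subjects still on study and progression-free at week 16 "will no longer be followed and will be censored for PFS at week 16". For DOR, Section 8.2.1 says that such subjects "will no longer be followed and will be censored for DOR at week 16". The DOR paragraph of Section 4.2.3.1.2 carries a censoring sentence that names only PFS and OS, so the DOR rule rests on Section 8.2.1.

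**Imaging.** The flow chart in Section 6.1 lists tumor imaging at screening, after Cycle 2 and at Cycle 4. Footnote 11 describes the last of these as "Performed at the end of Cycle 4, before the end of study visit". Section 7.1.2.6 puts it at 12 weeks. The only later scan it mentions is an optional repeat, at least 28 days on, for subjects who already show progression at week 12. The End of Study visit (week 16, ±10 days) has adverse event review, a directed examination and blood tests, but no imaging.

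**Summaries.** Sections 8.2 and 8.2.3 plan Kaplan-Meier medians with 95% CIs for PFS, DOR and OS.

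**Horizons.** Section 3.2 attaches week 12 to PFS and DOR and week 16 to OS. Section 2.1 takes all three to week 16. Section 8.2 allows follow-up to one year from Cycle 1 Day 1.

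**The concern.** A subject who is clear on the week-12 scan is credited with four more progression-free weeks in which radiographic progression cannot be seen unless symptoms prompt a scan. The PFS curve is therefore close to flat over that stretch by design, whatever the regimen does.

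DOR is hit harder. Section 2.1 determines response from the week-12 scan, so a response first recorded there meets no further scheduled assessment before it is censored. The DOR definition ends only at progression and does not count death, so even deaths in those weeks would not bring the curve down. Responses would look durable without having been tested for durability.

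**Working it through.** **A figure to reproduce.** The plan states no PFS or DOR rate, median or event count. Its only stated operating figures belong to the three-stage ORR design. An exact binomial recursion gives 0.0997, 0.9057 and 0.7857 against the stated 0.100, 0.906 and 0.786. They agree and play no part in what follows.

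**Length of the unscanned interval.** (16 − 12) × 7 = 28 days nominally. If the scan takes the week-12 visit window (±5 days, my assumption) and the censoring date is the actual week-16 visit (±10 days), the gap runs from 28 − 15 = 13 to 28 + 15 = 43 days.

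**Largest overstatement at week 16.** Assume exponential PFS with median m weeks (months × 52/12), so S(t) = 2^(−t/m). If nothing is found after the week-12 scan, the curve at week 16 still reads S(12), while the truth is S(16).

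| Assumed median | S(12) | S(16) | Difference | × 48 subjects |
|---|---|---|---|---|
| 4 months | 0.619 | 0.527 | 9.1 points | 4.4 |
| 6 months | 0.726 | 0.653 | 7.3 points | 3.5 |
| 8 months | 0.787 | 0.726 | 6.0 points | 2.9 |
| 10 months | 0.825 | 0.774 | 5.1 points | 2.5 |
| 12 months | 0.852 | 0.808 | 4.4 points | 2.1 |

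If half of these events surface clinically, the differences halve (3.7 points at 6 months, 2.2 at 12). If the trial stops at 11 or 30 subjects, the unseen events number 11 × 0.044 to 11 × 0.073 = 0.5 to 0.8, or 30 × 0.044 to 30 × 0.073 = 1.3 to 2.2.

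**Will the planned median be reached?** I used 1,000 simulated trials of 48 subjects per setting, with scans at weeks 6 and 12 and 0, 25% or 50% of events found without a scan. Under week-16 censoring the median was reached in at most 0.5% of trials for assumed medians of 6 months or more, and in 6% to 19% at 4 months.

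**Does moving the censoring date to the last scan cure it?** Not alone. At an assumed 6-month median:
- With no event seen after week 12, the curve at week 16 averages 0.727 under either rule, against a true 0.653.
- With 25% of events found clinically, week-16 censoring gives 0.706 and last-scan censoring gives 0.290. Event-free subjects have left the risk set, so even one later event takes the curve to zero. Check: the chance that no such event occurs is (1 − 0.25 × 0.0735)^48 ≈ 0.41, and 0.41 × 0.726 ≈ 0.30.
- Read at week 12 only, the curve averages 0.727 against a true 0.726.

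**DOR.** A response first documented at week 12 receives 28 days with no later scan, and 0 days if censored at the last scan. If the week-6 scan may document response, the figures are 70 and 42 days.

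**The case against.** **No week-16 PFS rate is planned.** A reader might infer that the trial will report an inflated week-16 PFS. The documents do not support that: they define medians only, and Section 3.2 attaches week 12 to PFS. This stands. But with the median usually not reached, what is left to show is the curve, and its last four weeks are the unscanned part.

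**The censoring date is not the cause.** A reader might call this a censoring-date error. The working shows otherwise: with no events seen after week 12, both dates give the same curve. The missing scan is the cause, and a change of date alone can do harm. This stands and shapes the fix.

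**The size is a ceiling on an assumed hazard.** Deaths and clinically evident progressions after week 12 still count for PFS, and Section 7.1 allows unscheduled procedures when clinically necessary. This stands.

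**Contact alone is not enough.** The PFS text asks that the contact document progression-free status. That is fair, but it names no assessment and none is scheduled.

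**Visit window.** A reader might also infer that a subject last seen at day 102 is carried forward to day 112. The week-16 rule covers subjects on study and progression-free at 16 weeks, and someone leaving sooner may fall under the last-contact clause. The text is unclear here rather than wrong.

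**Conclusion.** The point holds in limited form. PFS between weeks 12 and 16 is biased upward, by at most about 4 to 7 percentage points at week 16 for assumed medians of 12 to 6 months (9 at 4 months). That assumes exponential PFS and no event found without a scan. For scale, the binomial 95% half-width for a rate of 0.726 in 48 subjects is 1.96 × √(0.726 × 0.274/48) = 0.126, so the bias is smaller than the sampling error, but it always runs in the favorable direction. For DOR no hazard assumption is needed: a response first seen at week 12 has no later scheduled assessment.

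These are descriptive secondary endpoints with no test attached. The primary ORR, its stopping rules and the safety analyses are unaffected. The change is worth making because it is cheap.

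**What to change.** In Sections 4.2.3.1.2, 8.2, 8.2.1 and 8.2.3:

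1. Estimate Kaplan-Meier PFS only through the week-12 scan and report it as a week-12 rate with a 95% CI, in place of a median that will rarely be reached.
2. Cut the PFS analysis at that scan for everyone. Censor event-free subjects at their last tumor assessment. List deaths and clinical progressions after the week-12 scan separately, outside the curve. Assign week-12 scan results to the nominal visit, so that subjects scanned a few days early do not leave the risk set before others' events.
3. State that DOR is not estimable beyond the last scan, and report it only where a later scan exists. Say how subjects treated beyond week 16 before Amendment V5 are handled, since they may have later scans.
4. Keep the actual last-contact date for OS censoring.
5. Reconcile the follow-up horizons in Sections 2.1, 3.2, 4.2.3.1.2, 8.2 and 8.2.1.

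The cost is protocol and SAP wording, with no new procedures. The trial gives up four weeks of nominal PFS follow-up and largely loses DOR for responses first seen at week 12. A week-16 PFS estimate would need tumor assessment at week 16, which the schedule does not include.
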